## SYNOPSIS

---

**TITLE:** A Randomized, Active-Controlled Study to Evaluate the Efficacy and Safety of Intravenous Sulbactam-ETX2514 in the Treatment of Patients With Infections Caused by *Acinetobacter baumannii-calcoaceticus* Complex

---

**PROTOCOL NUMBER:** CS2514-2017-0004

---

**INVESTIGATIONAL PRODUCT:** Sulbactam-ETX2514 (ETX2514SUL)

---

**PHASE:** 3

---

**INDICATION(S):** Treatment of serious infections caused by *Acinetobacter baumannii* (*A. baumannii*)-*calcoaceticus* complex (ABC)

---

### OBJECTIVES:

This is a 2-part study, with Part A being the randomized, controlled portion of the study in patients with ABC hospital-acquired bacterial pneumonia (HABP), ventilator-associated bacterial pneumonia (VABP), ventilated pneumonia (VP), or bacteremia. Part B is the single-group portion of the study and includes ABC infections that are resistant to or have failed colistin or polymyxin B treatment, as detailed in the inclusion criteria.

The primary objectives of this study are the following:

- To compare the efficacy of ETX2514SUL plus imipenem/cilastatin to colistin plus imipenem/cilastatin in patients with carbapenem-resistant ABC (CRABC) infections in Part A; and
- To compare the incidence of nephrotoxicity, as measured by the Risk–Injury–Failure–Loss–End-stage renal disease (RIFLE) criteria, of ETX2514SUL to colistin in patients with ABC infections in Part A.

The secondary objectives of this study are the following:

- To compare the efficacy of ETX2514SUL plus imipenem/cilastatin to colistin plus imipenem/cilastatin in all randomized patients in Part A;
  - To evaluate the efficacy of ETX2514SUL plus imipenem/cilastatin in patients with colistin- or polymyxin B-resistant ABC infections in Part B;
  - To estimate the efficacy of ETX2514SUL plus imipenem/cilastatin for each primary infection site;
  - To evaluate and compare the safety of ETX2514SUL and colistin;
  - To describe the overall safety profile of ETX2514SUL; and
  - To determine the systemic exposure of ETX2514 and sulbactam in a small cohort of severely ill patients administered ETX2514SUL in Part A.
-

---

The exploratory objectives of this study are the following:

- To evaluate the efficacy of ETX2514SUL in relation to pharmacokinetics (PK) exposure;
  - To evaluate the efficacy of ETX2514SUL in relation to minimum inhibitory concentration (MIC) distribution of ETX2514SUL;
  - To evaluate the efficacy of ETX2514SUL in relation to total duration of treatment received; and
  - To compare the resource utilization of patients receiving ETX2514SUL plus imipenem/cilastatin to patients receiving colistin plus imipenem/cilastatin.
- 

## **POPULATION:**

The population for this study is male and female patients  $\geq 18$  years of age with documented ABC infections.

---

## **INCLUSION CRITERIA:**

### **General Inclusion Criteria:**

Patients who meet all of the following general inclusion criteria, in addition to the specific inclusion criteria listed below for Parts A and B, will be eligible to participate in the study:

1. A signed informed consent form;

Note: If a study patient is unable to provide informed consent due to their medical condition, the patient's legally authorized representative may consent on behalf of the study patient, or the decision can be made according to the procedure permitted by local law and institutional Standard Operating Procedures.

2. Male or female  $\geq 18$  years of age;
3. A confirmed diagnosis of a serious infection and the expectation, in the judgment of the Investigator, that the patient's infection will require treatment with intravenous (IV) antibiotics;
4. A known infection caused by ABC (bacteremia, HABP, VABP, VP, complicated urinary tract infection [cUTI] or acute pyelonephritis [AP], or surgical or post-traumatic wound infections) as either a single pathogen or member of a polymicrobial infection based on evidence from culture or, if available, rapid diagnostic test from a sample collected within 72 hours prior to randomization (HABP/VABP/VP patients), AND 1 of the following:
  - a. Has received no more than 48 hours of potentially effective (ie, Gram negative coverage) antimicrobial therapy prior to the first dose of study drug; OR
  - b. Is clinically failing prior treatment regimens (ie, clinical deterioration or failure to improve after at least 48 hours of antibiotic treatment);

Note: Rapid testing of respiratory specimens utilizing Biofire® FilmArray® 2.0 Pneumonia Panel (BPP) technology should be used to enable early identification of ABC pneumonia. Patients can be randomized based on the results of the BPP rapid test while awaiting results of cultures from the local laboratory. However, if the respiratory sample does not grow ABC in the local microbiology laboratory culture, these patients will be withdrawn from the study drug treatment.

Note: Isolation of ABC from pleural effusion (empyema) is allowed, if concurrent pulmonary infiltrate is confirmed.

5. Acute Physiology and Chronic Health Evaluation (APACHE) II score between 10 and 30, inclusive, OR Sequential Organ Failure Assessment (SOFA) score between 7 and 11, inclusive, at the time of diagnosis of infection. Patients who are not being treated in an intensive care unit and cannot have an APACHE II or SOFA score performed should have a quick SOFA (qSOFA) score  $\geq 2$  for enrollment;
6. Expectation, in the judgment of the Investigator, that the patient will benefit from effective antibiotic therapy and appropriate supportive care for the anticipated duration of the study; and
7. Women of childbearing potential (ie, not post-menopausal or surgically sterilized) must have a negative highly sensitive urine or serum pregnancy test before randomization. Participating women of childbearing potential must be willing to consistently use one highly effective method of contraception (ie, condom, combined oral contraceptive, implant, injectable, indwelling intrauterine device, or a vasectomized partner) from Screening until at least 30 days after administration of the last dose of study drug.

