
 
• Isolation of ABC from at least 1 blood culture collected from a peripheral vein OR newly placed intravenous line.
 
	
 
• Fever [1] (oral or tympanic temperature <math>\geq 38^{\circ}\text{C}</math> [<math>\geq 100.4^{\circ}\text{F}</math>] or rectal/core temperature <math>\geq 38.3^{\circ}\text{C}</math> [<math>\geq 100.9^{\circ}\text{F}</math>]) OR hypothermia (rectal/core temperature <math>< 35^{\circ}\text{C}</math> [<math>< 95^{\circ}\text{F}</math>]);
 
• Elevated total peripheral WBC count (<math>> 10,000/\text{mm}^3</math>);
 
• <math>> 15\%</math> immature neutrophils (bands) regardless of total peripheral WBC count;
 
• Leukopenia (total WBC count <math>< 4500/\text{mm}^3</math>);
 
• Tachycardia <math>> 100</math> bpm;
 
• Tachypnea <math>> 25</math> breaths/minute; OR
 
• Hypotension, systolic <math>< 90</math> mmHg.
 

1. Evidence of fever within 24 hours of the Screening Visit is acceptable if observed and documented by a healthcare provider.
 
ABC = Acinetobacter baumannii-calcoaceticus complex; bpm = beats per minute; WBC = white blood cell.
	

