4.1.2 Part A-Specific Inclusion Criteria

In addition to those general inclusion criteria listed in [Section 4.1.1](#), patients may enroll in Part A if they meet the criteria below. All patients must be categorized in 1 infection type that is judged to be the primary infection by the Investigator:

1. Diagnosed with HABP, VABP, VP, and/or bacteremia, defined as:

HABP With ABC in Sputum/Respiratory Sample		
All of the following:	AND signs or symptoms evidenced by at least 2 of the following:	AND at least 1 of the following:

 
Onset of symptoms >48 hours after admission or ≤7 days after discharge from an inpatient acute or chronic care facility (eg, LTAC, rehabilitation center, hospital, or skilled nursing home); OR
 
Admission from LTAC or rehabilitation center, or admission from home <7 days after discharge from an LTAC or rehabilitation center; AND
 
New or evolving infiltrate on chest X-ray, MRI, CT scan, or ultrasound obtained within 48 hours prior to randomization. Note: If an ultrasound is performed, a confirmatory X-ray or CT scan should be performed within 24 hours.
 
	
 
A new onset of cough (or worsening of baseline cough);
 
Auscultatory findings consistent with pneumonia/pulmonary consolidation (eg, rales, dullness on percussion, bronchial breath sounds, or egophony);
 
Dyspnea, tachypnea, or respiratory rate >25 breaths/minute; OR
 
Hypoxemia (oxygen saturation <90% or pO2 <60 mmHg while breathing room air, or worsening of the oxygen saturation/ FiO2); OR the following ALONE:
 
New onset need for mechanical ventilation.
 
	
 
Fever [1] (oral or tympanic temperature ≥38°C [≥100.4°F] or rectal/core temperature ≥38.3°C [≥100.9°F]) OR hypothermia (rectal/core temperature <35°C [<95°F]);
 
Elevated total peripheral WBC count (>10,000/mm^3);
 
>15% immature neutrophils (bands) regardless of total peripheral WBC count; OR
 
Leukopenia (total WBC count <4500/mm^3).
 

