## 4.2 Exclusion Criteria

Patients who meet any of the following criteria will be excluded from participation in the study:

1. Presence of suspected or confirmed deep-seated infection (eg, lung abscess in patients with pneumonia, skin abscess, or decubitus ulcer) that is not planned on being drained or debrided within 24 hours after randomization;

Note: Patients with an empyema who will have drainage within 24 hours of Screening and who are expected to be able to be treated with 14 or fewer days of antibiotics are allowed.

2. Evidence of active concurrent pneumonia requiring additional antimicrobial treatment caused by *Streptococcus pneumoniae*, *Haemophilus influenzae*, *Staphylococcus aureus*, *Mycoplasma pneumoniae*, *Chlamydia pneumoniae*, *Legionella pneumophila*, respiratory syncytial virus,

influenza and parainfluenza viruses, Middle East respiratory syndrome coronavirus, mycobacteria, aspergillus, mucormycosis, etc;

Note: If these organisms are identified but it is deemed by the Investigator that no treatment is warranted and their presence does not significantly change the prognosis of the patient, then the patient may be considered for this study.

3. Pulmonary disease that precludes evaluation of a therapeutic response (such as lung cancer resulting in bronchial obstruction or on the same side as the pneumonia, active tuberculosis, cystic fibrosis, granulomatous disease, fungal pulmonary infection, lung abscess, pleural empyema, post obstructive pneumonia, or COVID-19 infection without clinical improvement);

Note: Patients with an empyema who will have drainage within 24 hours of Screening and who are expected to be able to be treated with 14 or fewer days of antibiotics are allowed.

4. Presence of suspected or confirmed deep seated bacterial infections such as bacterial Gram negative osteomyelitis, endocarditis, or meningitis requiring prolonged therapy, as determined by history and/or physical examination;
5. Acute infective endocarditis due to Gram positive bacteria that require urgent/emergent indication of surgery (ie, heart failure because of valvular insufficiency or septic shock), or patients in whom surgery is contraindicated due to prohibitive risk for surgery due to comorbidities;
6. Irremovable implantable device or line thought to be the potential source of ABC infection;
7. Sustained shock with persisting hypotension requiring vasopressors to maintain mean arterial pressure (MAP)  $\geq 60$  mmHg;

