### 4.3 Withdrawal and Discontinuation Criteria

Participation of a patient in this clinical study may be withdrawn or study drug discontinued by the patient or Investigator for any of the following reasons:

- The patient withdraws consent or requests discontinuation from the study for any reason;
- Occurrence of any medical condition or circumstance that exposes the patient to substantial risk and/or does not allow the patient to adhere to the requirements of the protocol;
- Any SAE, clinically significant adverse event, severe laboratory abnormality, intercurrent illness, or other medical condition which indicates to the Investigator that continued participation is not in the best interest of the patient;
- Patient develops severe liver-related abnormalities, as detailed below:
  - ALT or AST  $>10 \times$  ULN;
  - ALT or AST  $>5 \times$  ULN for more than 2 weeks or progressively increasing transaminases despite clinical improvement of underlying infection;
  - Confirmed values of ALT or AST  $>3 \times$  ULN and total bilirubin  $>2 \times$  ULN or international normalized ratio  $>1.5$  (for patients who are not on coumadin) without evidence of an alternative etiology; or
  - Confirmed values of ALT or AST  $>3 \times$  ULN along with signs or symptoms compatible with hepatitis or hypersensitivity (eg, fatigue, nausea, vomiting, right upper quadrant pain or tenderness, jaundice, fever, rash, or eosinophilia [ $>5\%$ ]);
- Pregnancy;
- Requirement of prohibited concomitant medications, including the need for antibiotics that have an overlapping Gram negative coverage other than study drugs;

Note: Patients who require antibiotic prophylaxis due to immunosuppression (eg, trimethoprim-sulfamethoxazole for prophylaxis against *Pneumocystis carinii* [*P. carinii*] pneumonia) may participate in the study.

- Patients randomized to Part A based on a positive screening of a respiratory sample for ABC by BPP rapid test, but subsequently do not have growth of ABC in their respiratory sample culture processed by the local microbiology laboratory;
- Patient failure to comply with protocol requirements or study-related procedures, including the need for treatment with study drug beyond 14 days; or
- Termination of the study by the Sponsor or the regulatory authority.

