### 5.4 Randomization and Blinding

Qualifying patients enrolling in Part A will be randomized in a 1:1 ratio to receive 1.0 g ETX2514/1.0 g sulbactam q6h plus 1.0 g imipenem/1.0 g cilastatin q6h or 2.5 mg/kg colistin q12h plus 1.0 g imipenem/1.0 g cilastatin q6h via the Interactive Response Technology (IRT) system. Patients enrolled in the study based on the positive BPP rapid test results but are found to not grow

ABC in respiratory specimen cultures by the local microbiology laboratory will be withdrawn from the study drug treatment as detailed in [Section 4.3](#).

Randomization in Part A will be stratified by indication (HABP/VABP/VP versus bacteremia), severity of illness (based on APACHE II [10 to 19 versus 20 to 30], SOFA [7 to 9 versus  $\geq 10$ ], or qSOFA [2 versus 3] score at Screening), and geography (China Mainland versus Rest of World). In the situation where a patient has more than one score reported, the scores will be used in the following order: APACHE, SOFA, and qSOFA. A quick reference guide will be provided that describes the IRT system and includes user instructions. Enrollment of HABP, VP, and bacteremia patients will be limited to a total of no more than 40% of patients in Part A, regardless of resistance.

The study data will be collected and handled as if it were a blinded study. The blinded assessor (see Section 5.4.2), the Sponsor, and the Sponsor's designees involved in medical and safety monitoring, data management, and other aspects of the study (eg, interpretation of the results) will be blinded to treatment assignment. Given the complexity of the regimens, the Principal Investigator, other care givers, the clinical research associate (CRA), and other site personnel (eg, study coordinators and pharmacy staff) will be unblinded (see Section 5.4.1). Patients will not be informed of their treatment assignment, and efforts will be made to keep patients naïve to their treatment throughout the course of the study.

Part B is open-label and not randomized; all patients enrolling in Part B will receive 1.0 g ETX2514/1.0 g sulbactam q6h plus 1.0 g imipenem/1.0 g cilastatin q6h.

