### 6.2 Screening Visit (-48 Hours to Day 1)

Screening can occur up to 48 hours before the first dose of study drug. All Screening procedures must be performed prior to randomization and the first dose of study drug (Day 1). All Screening laboratories will be performed at the local laboratory and may have been collected as standard of care within 48 hours prior to randomization, with the exception of serum creatinine determination, which must be obtained at the local laboratory within 24 hours before the first dose of study drug.

The following procedures will be performed at Screening:

- Obtain informed consent;
- Review all inclusion and exclusion criteria;
- Only for patients suspected to have HABP/VABP/VP, perform rapid testing of respiratory specimens using BPP to detect ABC infection as specified in [Section 7.7.1](#) and the Laboratory Manual;
  - For patients who only signed the limited scope ICF (which only allows rapid testing on a respiratory sample):
    - If the BPP rapid test is negative or indeterminate for ABC, the patient should be screen failed;
    - If the BPP is indeterminate, the Investigator may opt to wait and repeat the test within 24 hours before screen failing the patient;  
  
Note: The Investigator should review the local culture result from the respiratory sample once available. If the local culture result is positive for ABC, the patient may be re-screened under a new patient number, beginning with the main ICF and ensuring all eligibility criteria are met.
  - For patients who signed the main ICF (including all study procedures):
    - If the BPP rapid test result is negative for ABC, the patient should not be screen failed immediately, instead the Investigator should wait for the local culture result. In case the local culture result is positive for ABC, the Investigator should proceed with the Screening procedures;

- Patients with suspected HABP/VABP/VP with a positive BPP rapid test for ABC of their respiratory specimen must meet all other enrollment criteria in order to be randomized. The respiratory specimen should be sent to the local laboratory for culture and susceptibility. If culture of the respiratory specimen by the local microbiology laboratory subsequently does not show growth with ABC, this patient must be withdrawn from the study treatment as they no longer meet eligibility criteria (see [Section 4.3](#));
- Obtain medical/surgical history;
- Record prior and concomitant medications;

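### Minor: a pneumonia patient enrolled on the rapid test whose respiratory culture is negative must stop study drug and leave the m-MITT even if a pre-dose blood culture grew ABC

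*Protocol*

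**What the plan says.** Pneumonia patients may be randomized on a positive BPP result while cultures are pending. General inclusion criterion 4 then adds that "if the respiratory sample does not grow ABC in the local microbiology laboratory culture, these patients will be withdrawn from the study drug treatment". The same rule stands in Protocol 3.1, 5.4, 6.6, 7.7 and 9.1 and in SAP 3.1, 3.3 and 8.3. Section 6.2 is the firmest and gives a reason: "this patient must be withdrawn from the study treatment as they no longer meet eligibility criteria". Section 4.3 is softer. It lists this event among the reasons for which "Participation of a patient in this clinical study may be withdrawn or study drug discontinued by the patient or Investigator". Protocol 9.1 and SAP 8.3 take these patients out of the m-MITT and keep them in the MITT and Safety Populations. No section makes an exception for ABC in blood.

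Part A also admits bacteremia. The culture requirement is "Isolation of ABC from at least 1 blood culture collected from a peripheral vein OR newly placed intravenous line", with at least one listed sign. Section 7.7 requires two sets of blood cultures from every patient at Screening. Section 7.7.2 accepts a positive blood culture from the 72 hours before randomization as a basis for enrollment.

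**The concern.** The rule looks at one specimen, although Part A can be entered on either of two. Because the blood cultures are drawn at Screening and BPP patients are randomized before culture results are known, a blood result that arrives after randomization is foreseeable.

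If blood grows ABC and the airway does not, the plan as written stops the randomized drug in a severely ill patient with culture-proven ABC bacteremia. It also removes that patient from the m-MITT and hence from the primary population. The stated ground is ineligibility, which may not be true.

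The plan describes no way back. Transfer to Part B requires colistin or polymyxin B resistance, and exclusion 26 bars re-enrollment of anyone already given ETX2514 in this study.

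**Working it through.** **Can the reason in 6.2 be false?** The pneumonia definitions require at least one of four systemic signs: fever or hypothermia, WBC above 10,000/mm³, more than 15% bands, or WBC below 4500/mm³. All four are also on the bacteremia sign list. A pneumonia patient with a qualifying ABC-positive blood culture therefore already has a bacteremia sign.

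**Is eligibility as bacteremia automatic?** No. Section 4.1.2 requires that "All patients must be categorized in 1 infection type that is judged to be the primary infection by the Investigator". ABC in blood without ABC in the airway also raises the question of another source. Exclusion 4 covers deep-seated infection such as "endocarditis, or meningitis requiring prolonged therapy, as determined by history and/or physical examination", and exclusion 6 covers an "Irremovable implantable device or line thought to be the potential source of ABC infection". So the reason is wrong for some of these patients, not for all.

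**The plan's own figures, for scale.** With mortality of 41% and 36% and a 20-point margin, the distance to the margin is 0.20 − (0.36 − 0.41) = 0.25. With unpooled variance, n per arm = (1.960 + 0.842)² × (0.41×0.59 + 0.36×0.64) / 0.25² = 7.849 × 0.4723 / 0.0625 = 59.3, so 60 per arm and 120 in total, with 80.5% power. Enrollment is 120 / 0.60 = 200. Both figures reproduce.

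**How many patients?** The documents give none of the rates needed, so the percentages below are assumptions except the 60%. The lower count of pneumonia patients comes from section 5.4: "Enrollment of HABP, VP, and bacteremia patients will be limited to a total of no more than 40% of patients in Part A". At most 0.40 × 200 = 80 can be bacteremia, leaving at least 120 with pneumonia.

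| Quantity | Low | Middle | High |
|---|---|---|---|
| Pneumonia patients in Part A | 120 | 160 | 200 |
| Enrolled on BPP | 25% | 50% | 75% |
| Respiratory culture negative | 5% | 15% | 30% |
| ABC in pre-dose blood | 2% | 8% | 15% |
| Affected by the rule (product) | 0.03 | 0.96 | 6.75 |
| × 0.60 carbapenem-resistant | 0.018 | 0.576 | 4.05 |

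The last row counts the patients whom a laboratory-only rule would add to the CRABC m-MITT, both arms together, before its other susceptibility exclusions. In the middle case the Poisson chance of none is 56%, of exactly one 32%, and of two or more 11%.

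If 50%, 80% or 100% of affected patients would also pass a full eligibility recheck, 0.015, 0.768 or 6.75 remain. Of these, 0.009, 0.461 or 4.05 are carbapenem-resistant.

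A coarser set of assumptions gives a similar range. Suppose 5–20% of all 200 patients are BPP-positive with a negative respiratory culture, and 5–20% of those have ABC in blood. Then 200×0.05×0.05 = 0.5 to 200×0.20×0.20 = 8 patients are affected, and 0.3 to 4.8 are carbapenem-resistant.

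**Effect of one patient on an arm of 60.**
- Control, 41% (24.6 deaths): an added death gives 25.6/61 = 41.97% (+0.97 points); an added survivor gives 24.6/61 = 40.33% (−0.67).
- Test, 36% (21.6 deaths): an added death gives 22.6/61 = 37.05% (+1.05); an added survivor gives 21.6/61 = 35.41% (−0.59).
- If the patient instead displaces another within a fixed 60, the shift is at most 1/60 = 1.67 points.

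**The case against.** The strongest defense is that the present rule is objective. Whether the local respiratory culture grew ABC needs no opinion. These patients were randomized under definitions that require ABC in a respiratory sample, so without growth the diagnosis they entered under is not culture-confirmed, and declining to reclassify after randomization is a legitimate choice. A remedy that asked the Investigator to decide whether bacteremia is primary, or whether a line is the source, would be worse: sections 5.4 and 5.4.1 leave the Investigator unblinded, and entry to the primary population would then rest on judgment made after randomization by someone who knows the arm. That part stands and shapes the fix below. It does not rescue the rule, because a rule reading pre-dose blood and respiratory cultures together is just as objective.

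It is also fair that no sentence says blood-positive patients are to be withdrawn. That follows from the absence of an exception. Section 4.3 is permissive, and the MITT paragraph speaks of a missing ABC culture without naming the specimen. But 6.2, 9.1 and SAP 8.3 name the respiratory culture, and the looser wording does not override them.

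The safeguards are real. The patient stays in the ITT, MITT and Safety Populations, Day 28 survival is collected, and 7.7 asks the Investigator to assess continued standard-of-care treatment.

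**Conclusion.** The point holds as a minor one. In a rare case the plan takes a patient off randomized drug and out of the m-MITT for a reason that can be false. The middle estimate is about one affected patient in Part A and about half a patient in the primary population (0.58 under a laboratory-only rule, 0.46 if full eligibility is also required). Both rest on assumed rates; only the 60% resistance figure is the plan's.

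A reader might infer three stronger things that the documents do not support:

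- That every such patient is wrongly withdrawn. Primary infection type and exclusions 4 and 6 mean some would be ineligible as bacteremia too.
- That the primary comparison is biased. The specimens that decide membership are taken before the first dose, so treatment cannot influence them.
- That power is lost. Enrollment continues until 120 patients are in the CRABC m-MITT.

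A shift of at most 1.7 points per patient in one arm is small beside the 20-point margin.

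**What to change.** Withdraw a BPP-enrolled patient for culture negativity, and exclude from the m-MITT, only when no accepted pre-dose respiratory specimen (7.7.1) and no accepted blood specimen (7.7.2: within 72 hours before randomization, peripheral vein or newly placed line) grew ABC.

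- Decide m-MITT and CRABC m-MITT membership from laboratory results alone, applying the resistance and 72-hour criteria to the blood isolate.
- Keep the randomization stratum, 40% cap category and baseline infection type as randomized.
- Use the 7.8.1 bacteremia rules for microbiologic outcome.
- Leave the Investigator free to stop study drug under 4.3 if another source, such as endocarditis or an irremovable line, is found, and state that this does not change m-MITT membership.

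The cost is a wording amendment in the Synopsis, Protocol 3.1, 4.1.1, 4.3, 5.4, 6.2, 6.6, 7.7 and 9.1, and SAP 3.1, 3.3 and 8.3. No new samples are needed: the Screening blood cultures are already required, and 7.7.2 already asks for daily repeats when baseline blood is positive. There are two downsides: an occasional mismatch between randomized indication and confirmed infection type, and an occasional m-MITT patient whose blood source would have been an exclusion.
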